5.12 Summary of Assessments

The schedule of visits and procedures to be conducted at each visit are summarized in the Schedule of Study Procedures.

Schedule of Study Procedures

5.13 Screen Failures

Screen failures will not be entered in the database or included in any data analyses. A screen failure is a subject who received information about the study, including signing an informed consent/assent, and possibly underwent some study-related procedures but was not enrolled, dispensed study medication, nor applied the investigational product.

5.14 Protocol Deviations/Violations

This study will be conducted as described in this protocol except for an emergency situation in which the protection, safety, and well-being of the subject requires immediate intervention, based on the judgment of the investigator or a responsible, appropriately trained and credentialed professional(s) designated by the investigator. In the event of a significant deviation from the protocol due to an emergency, accident or mistake, the investigator or designee must contact Perrigo / [REDACTED] contacts in Section 15 (Appendix A) of this protocol at the earliest possible time.

[REDACTED]

5.15 Subject/Treatment Compliance

Study personnel will ensure that subjects can identify the secondarily infected target lesion they will be treating and know where to apply the study medication. Subjects will be instructed on the correct use of study medication at the study site during Visit 1/Day 1. Subjects will apply the first application at the study site under the supervision of site staff. Subjects will be instructed to apply [REDACTED] study medication three (3) times per day for ten (10) consecutive days according to the Subject Instructions [REDACTED]

[REDACTED]

[REDACTED]

[REDACTED]

[REDACTED]

[REDACTED]

[REDACTED]

[REDACTED]

5.16 Discontinuation/Withdrawal of Study Subjects

Subjects may be removed from the study for any of the following reasons:

- Negative baseline culture.
- The subject withdraws his or her consent for any reason.
- The subject's condition has worsened to the degree that the investigator feels it is unsafe for the subject to continue in the study or requires an alternative therapy for the treatment of their secondarily infected traumatic skin lesion.
- The subject's medication code is unblinded.
- The subject did not meet or no longer meets the entry criteria.
- An adverse event, including intercurrent illness, occurs for which the subject desires to discontinue treatment or the investigator determines that it is in the subject's best interest to be discontinued.
- A concomitant therapy is reported or required that may interfere with the results of the study.
- The subject is lost to follow-up. The investigator will document efforts to attempt to reach the subject twice by telephone and will send a certified follow-up letter before considering that subject lost to follow-up. All attempts must be thoroughly recorded.
- The subject becomes pregnant during the course of the trial.
- A lack of treatment response, [REDACTED]
[REDACTED]
- Investigator discretion (e.g., non-compliant with study protocol requirements).

After a subject has been discontinued, he/she will not be allowed to re-enroll in the study at any facility.

The reasons for a subject being discontinued will be documented in the eCRFs and the enrollment log.

If a subject is discontinued from the study for any reason, the Visit 4/Day 17 (End of Study Visit/Early Termination Visit) procedures should be completed and any outstanding data and study medication should be collected. Data, in addition to the reason for discontinuation and the date of removal, will be recorded on the Source Document and End of Study eCRF.

If a subject discontinues from the study at any time due to an adverse event, the reason for discontinuation, the nature of the event, and its clinical course must be fully documented. For such a subject, the investigator must strive to follow the subject until the adverse event has resolved, become clinically insignificant, is stabilized, or the subject is lost to follow-up.

[REDACTED]
[REDACTED]
[REDACTED]
[REDACTED].

6. MATERIALS AND SUPPLIES

6.1 Study Medication

The study medication supplied by Perrigo will consist of:

Test Product: Mupirocin Cream USP, 2%,

Perrigo

Reference Product: Mupirocin Cream USP, 2% (manufactured by Glenmark Pharmaceuticals)

Vehicle: Vehicle of test product

Perrigo

[figure not shown]
6.2 Medication Management

Labeling, Packaging and Distribution

The study medication assigned to each subject number will be determined by a computer-generated randomization schedule. Study medication is labeled and packaged, according to the randomization code, so that neither the subject nor the investigator can identify the treatment.

The tear-off portion of each kit label contains the identity of the medication in the tube. The investigator will not remove the occluding layer of the label unless absolutely necessary to provide medical treatment to a subject in an emergency and preferably with prior authorization from Perrigo or designee, whenever possible. If the occluded portion of the label is removed, each involved subject(s) will be discontinued from the study and the reason will be noted on the source documents and eCRFs.

The tear-off portion has an adhesive backing to affix to the study medication dispensing log that will be maintained at the investigator site. **THE LOG AND TEAR-OFF LABELS WILL BE STORED SECURELY AT THE STUDY SITE AS RECORD OF THE SUBJECT'S INTENDED TREATMENT. THE STUDY LABEL FORMS AND THE ATTACHED ORIGINAL LABELS SHOULD NOT BE REMOVED FROM THE SITE UNTIL PERRIGO HAS NOTIFIED THE SITES, IN WRITING.**

Retention Samples

Each investigational site where study medication is dispensed to at least one subject will be required to randomly select one block of study medication [REDACTED] to be maintained as retain samples. The investigator will maintain one randomly selected block of study medication from each shipment of study medication received. As per the Code of Federal Regulations Part 21, Section 320.38(e), "Each reserve sample shall be stored under conditions consistent with product labeling and in an area segregated from the area where testing is conducted and with access limited to authorized personnel (stored between 20° to 25°C (68° to 77°F).; even after the study has concluded. Each reserve sample shall be retained for a period of at least five (5) years following the date on which the application or supplemental application is approved, or, if such application or supplemental application is not approved, at least five (5) years following the date of completion of the bioavailability study in which the sample from which the reserve sample was obtained or was used." The investigator will store the retain sample study medication until such time as written notification is received from Perrigo that the samples are no longer required.

Storage and Test Article Accountability

Study articles used to conduct this study will be maintained under adequate security by the investigator or designee. Each investigator site will ensure that the temperature of study medication is monitored and recorded throughout the study. The study medication should be stored between 20° to 25°C (68° to 77°F) and should not be frozen, as recommended in the labeling for Mupirocin Cream USP, 2%. The medication should be kept away from children unless the subject is a child. The investigator will not supply study medication to any person not enrolled in this study, or to any physician or scientist except those named as sub-investigators.

The clinic personnel at each investigator site will keep a running inventory of study medication dispensed that will include subject numbers assigned and the date each tube of study medication is dispensed and returned. A study medication accountability form will be provided to the investigator to document all medications received, dispensed by and used by each subject. At the conclusion of the study all unused, partially used, and empty tubes must be inventoried by the monitor and returned to Perrigo, or designee, for destruction, with the exception of retention samples which shall remain at the investigator site.

Randomization

Randomization will be performed according to a computer-generated randomization scheme where the treatment group designation has been assigned to the subject number. The treatment designation will remain blinded until the final database is closed. An independent third party will hold the randomization code throughout the study. The randomization scheme will be a block randomization, with each block of [REDACTED] assigned to Test: Reference: Vehicle [REDACTED].

Procedure for Breaking the Blind

The investigator, staff at the study site, study monitors, and data analysis/management personnel are blinded to the subject assignment. In the event of an emergency, the specific subject treatment may be identified by removing the overlay of the blinded label for each subject at each investigator site, which is attached to the study medication log; however, every effort should be made to maintain the blind. **The investigator must not scratch off the occluding layer of the label unless absolutely necessary to provide medical treatment to a subject in an emergency situation only and should seek prior authorization by Perrigo or designee when possible.** The reason for breaking the blind must be clearly documented in the source documentation and eCRF and the subject must be discontinued from the study. Perrigo must be notified immediately upon all unblinding situations.

7. ADVERSE REACTIONS

The potential adverse reactions of generic Mupirocin Cream USP, 2%, are anticipated to be similar to those observed with Mupirocin Cream USP, 2%.

The adverse reactions reported by at least 1% of 339 subjects in connection with the use of Mupirocin Cream USP, 2% in clinical trials were headache (1.7%), rash (1.1%), and nausea (1.1%). Adverse reactions that occurred in less than 1% of subjects were abdominal pain, burning at application site, cellulitis, dermatitis, dizziness, pruritus, secondary wound infection, and ulcerative stomatitis.

Systemic allergic reactions, including anaphylaxis, urticaria, angioedema, and generalized rash, have been identified during postmarketing use of Mupirocin Cream USP, 2%. Because they are reported voluntarily from a population of unknown size, estimates of frequency cannot be made.

Clostridium difficile-associated diarrhea (CDAD) has been reported with use of nearly all antibacterial agents and may range in severity from the mild diarrhea to fatal colitis.

7.1 Departure from the Protocol for Individual Subjects

When an emergency occurs requiring a departure from the protocol for a subject, departure will be only for that subject. In such circumstances, the investigator or other physician in attendance will contact the Medical Monitor or Perrigo by telephone and follow-up with a written description as soon as possible. The overseeing IRB should also be notified.

7.2 Definitions

An adverse event (AE) is defined as any untoward medical occurrence in a subject administered a medicinal product and which does not necessarily have to have a causal relationship with this

Protocol No: PRG-NY-19-002

treatment. An adverse event can therefore be any unfavorable and unintended sign (for example, an abnormal laboratory finding), symptom, or disease temporally associated with the use of a medicinal product, whether or not considered related to this medicinal product.

A serious adverse event (SAE) is an adverse event that results in any of the following outcomes:

- Death
- Life-threatening event (e.g., the subject was, in the opinion of the investigator, at immediate risk of death from the event as it occurred. It does not include an event that, had it occurred in a more severe form, might have caused death)
- Requires in-subject hospitalization or prolongs hospitalization
- A persistent or significant disability/incapacity or substantial disruption of the ability to conduct normal life functions
- Congenital anomaly/birth defect
- Other adverse events that may be considered serious based upon appropriate medical judgment, may jeopardize the subject and may require medical or surgical intervention to prevent one of the outcomes listed above.

Immediately Reportable Adverse Events (IRAE): Any serious AE or any AE that necessitates discontinuation of study medication, including pregnancy.

Unexpected Adverse Event: An unexpected event is any adverse drug experience, the specificity or severity of which is not consistent with the current approved product labeling (package insert) for the study medication, the Investigator's Brochure, or as described in the clinical protocol and consent materials.

Intensity of Adverse Events: The maximum intensity of an AE during a day should be recorded on the eCRF. If the intensity of an AE changes over a number of days, then separate entries should be made having distinct onset dates for the changes in severity.

Mild - AEs are usually transient, requiring no special treatment, and do not interfere with subject's daily activities.

Moderate - AEs typically introduce a low level of inconvenience or concern to the subject and may interfere with daily activities, but are usually ameliorated by simple therapeutic measures.

Severe - AEs interrupt a subject's usual daily activity and traditionally require systemic drug therapy or other treatment.

Causal Relationship to Study Medication: The following criteria should be used in assessing the apparent causal relationship of an AE to study medication.

Definitely - The AE:

- follows a reasonable temporal sequence from study medication administration
- abates upon discontinuation of the study medication (dechallenge)

- is confirmed by reappearance of the reaction on repeat exposure

Probably - The AE:

- follows a reasonable temporal sequence from study medication administration
- abates upon discontinuation of the study medication (dechallenge)
- cannot be reasonably explained by the known characteristics of the subject's state.

Possible - The AE:

- follows a reasonable temporal sequence from study medication administration
- but that could readily be produced by a number of other factors.

Unlikely - The AE:

- follows a reasonable temporal sequence from study medication administration.
- could have been produced by either the subject's clinical state or by study medication administration.

Not related - The AE:

- does not have a reasonable temporal association with the administration of study medication
- has some other obvious explanation for the event.

7.3 Eliciting and Reporting of Adverse Events

The investigator will periodically assess subjects for the occurrence of adverse events. [REDACTED]

[REDACTED] All adverse events (as defined in Section 7.2), either observed by the investigator or one of his/her medical collaborators, or reported by the participant spontaneously, or in response to direct questioning, will be reported and documented in the source document and the study reporting forms. When reporting an adverse event, the investigator must assign a severity grade to each event and declare an opinion on the relatedness of the event to the study medication or procedure. Serious or unexpected adverse events must be reported to [REDACTED] **within 24 hours** of when the investigator first learns of the occurrence of the event.

Adverse events will be documented in the source document and recorded in a timely manner on the eCRFs. Adverse events that are identified at the last assessment visit (or the early termination visit) must be recorded on the AE eCRF with the status of the AE noted.

Adverse event reporting begins from the signing of informed consent/assent. Adverse events should be followed until resolved or 30 days after the final study treatment. In any case, serious adverse events that are not resolved or considered to be chronic within 30 days of the final study treatment must be followed by the investigator until they become resolved or are considered to be chronic (stabilized for at least 30 days). All events that are ongoing at this time will be recorded as ongoing on the eCRF.

Expedited Reporting Responsibilities of the Study Center

For any serious or unexpected adverse event, [REDACTED] must be notified **within 24 hours** of when the investigator first learns of the occurrence of the event. Expedited reporting requirements for serious adverse events are described below. Adequate information must be collected with supporting documentation to complete a standard report for submission to Perrigo. The adverse event term on the AE eCRF and the SAE report should agree exactly. Special attention should be given to recording hospitalizations and concomitant medications.

Subjects with unresolved adverse event(s) or serious adverse event(s) should be followed by the investigator until the events are resolved, events determined to be chronic, or the subject is lost to follow-up. Resolution means the subject has returned to the baseline state of health, or the investigator does not expect any further improvement or worsening of the adverse event. The investigator should continue to report any significant follow-up information to the sponsor up to the point that the event has resolved. Any serious adverse event reported by the subject to the investigator that occurs within 30 days after the last assessment and is determined by the investigator to be reasonably associated with the use of the study medication, should be reported to the sponsor within 24 hours of when the investigator first learns of the occurrence of the event.

When reporting an SAE the investigator (or the Study Coordinator) will promptly report any serious adverse event or pregnancy by telephone to [REDACTED] [REDACTED] immediately after the investigator becomes aware of the event. An SAE form should be completed and sent by fax, email, or overnight courier to [REDACTED] within 24 hours of knowledge of the event by the site. In many cases, only preliminary information will be available. Appropriate follow-up information should be sought (hospital discharge summaries, operative reports, etc.) and a follow-up SAE report form submitted. A designation of causality from the study medication should always be included with a follow-up report. Assess and report the causality of the event.

Submitting an Expedited Safety Report to the IRB

Once [REDACTED] receives all supporting documentation for the reported event, the Medical Monitor, in conjunction with Perrigo, will determine if the safety report is eligible for expedited review. [REDACTED] will log the initial event and will notify the sponsor that an event has been reported within 1 business day after initial receipt. [REDACTED] will complete the review of the event. This form, as well as other supporting documentation, will be forwarded to [REDACTED] Medical Monitor for review. [REDACTED] will finalize the report and distribute it to the sponsor within 1 day (one) after initial receipt. When expedited safety reporting to regulatory authorities is indeed required, the investigator should review and update any newly available materials at once. Follow-up queries may be sent to the study center to further clarify the event.

Each expedited safety report will routinely include a brief cover memorandum, the completed report, and any additional pertinent information recommended by [REDACTED], Perrigo, or the study Medical Monitor. Once the report is assembled, the Principal Investigator must submit the expedited safety report to the IRB within the required reporting timeframe. Follow-up reports should be submitted when requested or when pertinent information becomes available.

When a Principal Investigator receives an expedited safety report from [REDACTED] or the sponsor detailing adverse events occurring at other study centers under this protocol, it must be promptly submitted to the study center's IRB. The Principal Investigator must retain a copy of such reports as submitted to his/her IRB in the site's study Regulatory Binder.

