7.4 SAE & AEs Requiring Discontinuation of Study Drug, including Pregnancies

ANY SAE THAT OCCURS AFTER A SUBJECT HAS ENTERED THE STUDY, WHETHER OR NOT RELATED TO STUDY MEDICATION, MUST BE REPORTED TO [REDACTED] IMMEDIATELY (WITHIN 24 HOURS) VIA TELEPHONE OR FACSIMILE. IF INITIALLY REPORTED VIA TELEPHONE, THIS MUST BE FOLLOWED-UP BY A FACSIMILE OF THE WRITTEN SAE REPORT WITHIN 24 HOURS OF THE CALL TO [REDACTED].

Non-serious events that require discontinuation of study medication (including laboratory abnormalities) should be reported to [REDACTED] immediately and within 1 working day.

Subjects who discontinue due to experiencing adverse events should be followed clinically until their health has returned to baseline status or until all parameters have returned to normal. It is expected that the investigator will provide or arrange appropriate supportive care for the subject.

A subject who experiences a severe adverse event related to study drug will be discontinued from the study.

The notification about any serious adverse event should be directed to:

[REDACTED]
[REDACTED]
[REDACTED]
[REDACTED]
[REDACTED]
[REDACTED]

[REDACTED] will report the SAE to the Sponsor:

SPONSOR

[REDACTED]
[REDACTED]
[REDACTED]
[REDACTED]
[REDACTED]
[REDACTED]
[REDACTED]
[REDACTED]
[REDACTED]

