7.5 Pregnancy

At the time the Principal Investigator or site personnel becomes aware that a study participant became pregnant during study participation, the Principal Investigator or designee will report the pregnancy immediately by phone and/or by faxing a completed Pregnancy Report to [REDACTED] within 1 business day of being notified of the pregnancy report.

The report will include the following elements:

- Participant (mother's) coded study identifier;
- Date of participant's last menstrual period;
- Total accumulated dose of study treatment administered to date;
- Date of study medication administration.

The investigator will follow the subject until completion of the pregnancy and must assess the outcome in the shortest possible time but not more than 30 days within completion of the pregnancy.

Upon delivery, miscarriage or abortion, the Principal Investigator or designee must forward a follow-up Pregnancy Report with any relevant information on the present condition of the fetus to the [REDACTED], including:

- Mother's coded study identifier(s);
- Gestational age at delivery, miscarriage or abortion;
- Birth weight, gender, length and head circumference, if available;
- Apgar scores recorded after birth, if available;
- Any abnormalities.

If the outcome of the pregnancy **meets the criteria for immediate classification of an SAE** (e.g., spontaneous or therapeutic abortion [any congenital anomaly detected in an aborted fetus is to be documented], stillbirth, neonatal death, or congenital anomaly), the investigator will report the event by phone and by faxing a completed SAE report form to [REDACTED] within 1 working day of being notified of the pregnancy report.

If the trial is completed before the outcome of the pregnancy is known, [REDACTED] will assume the responsibility for following up on the pregnancy. [REDACTED] will contact the investigator or Study coordinator on or around the potential expected date of delivery to follow-up on the outcome of pregnancy and will also check on the status of the infant 8 weeks post-delivery. Upon awareness of the pregnancy outcome and known status of the infant following 8 weeks of delivery, the investigator will complete the applicable pregnancy report forms and fax to [REDACTED] within 1 day of being notified.

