7.6 Post Study Adverse Events

Non-serious Adverse Events

Adverse events that are identified at the last assessment visit (or the early termination visit) must be recorded on the AE eCRF with the status of the AE noted. These adverse events must be followed by the investigator until the events are resolved, events determined to be chronic or the subject is lost to follow-up. Resolution means the subject has returned to the baseline state of health or the investigator does not expect any further improvement or worsening of the adverse event.

Serious Adverse Events

Serious adverse events that are identified on the last assessment visit (or the early termination visit) must be recorded on the AE eCRF page and reported to Perrigo according to the procedures outlined above. Subjects with unresolved previously reported serious adverse events, or any new serious adverse events identified on the last assessment visit, should be followed by the investigator until the events are resolved, or the subject is lost to follow-up. Resolution means the subject has returned to the baseline state of health or the investigator does not expect any further improvement or worsening of the adverse event. The investigator should continue to report any significant follow-up information to Perrigo up to the point that the event has resolved. Any serious adverse event reported by the subject to the investigator that occurs after the last assessment and is determined by the investigator to be reasonably associated with the use of the study drug, should be reported to Perrigo.

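### Do the differing end points for adverse-event follow-up, and the differing deadline for pregnancy-outcome SAEs, call for a change to the plan?

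*Protocol*

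**What the plan says.** **Length of follow-up.** Protocol 7.3 gives a general rule, "Adverse events should be followed until resolved or 30 days after the final study treatment", extends it for serious events until they resolve or become chronic, and adds: "All events that are ongoing at this time will be recorded as ongoing on the eCRF". Later in 7.3, under the sub-heading on expedited reporting, subjects with unresolved events, serious or not, "should be followed by the investigator until the events are resolved, events determined to be chronic, or the subject is lost to follow-up". Section 7.6 says of non-serious events identified at the last or early termination visit that they "must be followed by the investigator until the events are resolved, events determined to be chronic or the subject is lost to follow-up". Both 7.3 and 7.6 count an event as resolved if health is back to baseline or if the investigator expects no further change.

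**Subjects who leave because of an adverse event.** Section 5.16 says "the investigator must strive to follow the subject until the adverse event has resolved, become clinically insignificant, is stabilized", with loss to follow-up as a further stop; redacted lines come after it. Section 7.4 says these subjects "should be followed clinically until their health has returned to baseline status or until all parameters have returned to normal".

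**Pregnancy outcomes that count as serious.** Section 7.5 asks for a telephone report and a faxed form "within 1 working day of being notified of the pregnancy report". Section 7.4 requires any SAE to be reported "IMMEDIATELY (WITHIN 24 HOURS) VIA TELEPHONE OR FACSIMILE". Section 7.3 also sets 24 hours, counted from when the investigator or site learns of the event, and wants an SAE or pregnancy telephoned immediately. Section 7.2 classes both as immediately reportable.

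**The concern.** A site that opened only the first part of 7.3 could stop following a non-serious event that 7.6 says must still be followed. A site that opened only 5.16 could stop at stabilization when 7.4 looks for a return to baseline. A site that opened only 7.5 could report a serious outcome later than 7.4 allows. In a multi-center trial this could mean different end dates and outcomes recorded for similar events, and deviations charged to sites that had obeyed one part of the protocol.

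The starting point in 7.5 adds to the doubt. The initial pregnancy report normally comes before the outcome, so it is not obvious when the clock starts. What is at stake is the completeness of safety follow-up and the speed of reporting.

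**Working it through.** There is no stated figure to reproduce. The check sets the passages side by side, sizes the gaps by date arithmetic, and traces what reaches an analysis.

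**1. The 30-day stop against the open-ended rule.**
- Stop day = last dose day + 30. With a last dose on Day 10: 10 + 30 = Day 40. Appendix B puts the End of Treatment visit at Day 10 to 12; if dosing ran to Day 12, the stop would be 12 + 30 = Day 42.
- Appendix B puts the Follow-up visit at Day 13 to 21. Day 40 is therefore 40 − 21 = 19 to 40 − 13 = 27 days after it.
- If the definition of resolution is applied throughout 7.3, an event that has settled counts as resolved under every passage. The conflict is left with non-serious events still open and still expected to change at about Day 40. The documents give no rate for these, so their number cannot be estimated.
- The instruction to record open events as ongoing is consistent with the 30 days being a data cutoff, although the text does not say so.

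**2. Section 5.16 against 7.4.**
- A subject whose finding is stable but abnormal has reached a stop under 5.16 and not under 7.4. That is a true difference.
- Both are softly worded: 5.16 asks the investigator to strive, and 7.4 says should. Return to baseline is resolution, so a site that reaches the 7.4 end point has also met 5.16. Section 7.4 names no stop for a subject who cannot be reached; 5.16 does.

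**3. One working day against 24 hours.** The protocol does not define a working day. Assume it means the same clock time on the next Monday-to-Friday day:

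| Site learns of outcome on | Limit | Excess over 24 h |
|---|---|---|
| Sunday to Thursday | 24 h | 0 h |
| Friday | 72 h | 48 h |
| Saturday | 48 h | 24 h |

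- The limit is longer on 2 of 7 days; holidays would add to it.
- On the starting point, the preceding text of 7.5 describes a follow-up Pregnancy Report sent after delivery, miscarriage or abortion. Its last paragraph, on outcomes after trial completion, asks for forms within one day of notification, on awareness of the outcome. The clock can therefore be read as starting when the outcome is known.

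**4. What reaches the analysis.**
- SAP 5.8 defines a treatment-emergent event by occurrence on or after the first dose, and SAP 6.1 applies its partial-date rules to the start date only. How long an event is followed does not move it in or out of the count.
- The test of Test against Reference in SAP 5.8 uses the proportion of subjects with any such event. The visible SAP has no analysis of event duration.
- The severity tables count a subject once per preferred term at the strongest grade. A cell could change only if an event already recorded worsened after the 30-day stop at a site that had stopped looking. These tables are descriptive, and under the double blind a site's reading of the rule applies to all three arms alike.
- Clinical and bacteriological cure are read at Visits 3 and 4, by Day 21 on the Appendix B window, before the Day 40 stop.

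**The case for a change.** The strongest case for a change is that 7.6 concerns non-serious events by its own heading. The difference from the first part of 7.3 therefore cannot be put down to one passage covering serious events and the other not. An event still changing after 30 days is treated differently by the two. Section 7.4 itself separates the clocks, with 24 hours for any SAE and one working day for non-serious events leading to discontinuation, so 7.5 places a serious outcome on the clock used elsewhere for non-serious ones. No visible sentence tells a site to apply the longest follow-up and the shortest deadline. The remedy would be only a wording amendment and a note to sites.

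Most of this stands as a description of the text. The three differences are real, and redaction does not explain the wording that can be seen. What does not stand is the step to a needed change. The broad definition of resolution removes most of the first conflict. The immediate telephone report in 7.3 and the 24-hour rule in 7.4 already cover any SAE, including a pregnancy outcome that counts as one. None of the passages forbids longer follow-up or earlier reporting, so they can all be met at once. An amendment that is not administrative would also have to wait for IRB approval under Protocol 10.2, with no result changed by it.

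**Conclusion.** No change to the plan follows. The wording is inconsistent in three places, and the differences are small: non-serious events still evolving about 30 days after the last dose, in unknown number; subjects who left for an adverse event and are stable but not back to baseline; and up to 48 extra hours on 2 of 7 days for pregnancy-outcome SAEs, before holidays.

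The effect on efficacy, sample size and the proportion with any treatment-emergent event is nil. At most, some listed end dates, ongoing flags and maximum severities could differ between sites.

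This rests on the visible text of 5.16 and 7.3, both partly redacted; on a last dose on Day 10 for the Day 40 figure; on a Monday-to-Friday working week; and on sites reading the safety sections together. Where the passages disagree, the sponsor must reconcile them and say which rule is intended, and this review takes no view on that. It is housekeeping that can accompany other protocol edits or site training.
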